5.8 Methods for processing, labeling and storage of serum samples

Approximately 1mL (500ul) of blood sample will be drawn from each participant (from forearm) during each visit, from which the parasites and their genetic material will be extracted. The blood samples will be collected before treatment administration on D0, and systematically during subsequent visits. To

minimize bleeding from collection site, an adhesive tape will be applied at the site of blood sample draw, according to local practice. Not more than two attempts should be made to draw the required volume of blood.

The blood will be processed and aliquoted and stored according to the Clinical Specimen Lab Manual. Each sample tube will be labeled with the labels provided for the study. Collected samples will be labeled by the main site investigator and with a code that only the study site can link to the participant's name. All stored research samples will be logged into a secure database. Any use of the samples will be documented. Complete instructions for labeling and storage of serum samples will be included in the Clinical Specimen Lab Manual, which will be stored in the Investigator Site File.

Testing of samples will be performed in the analyses site set up at the various study sites. Samples will be retained in accordance with regulatory guidance for retention of essential study documents as described in SECTION 12 of this protocol. Participants will be informed and asked to agree to long term storage of specimens for use in future research through a specific consent form. At study closure, the study coordinators/sonsor will designate a storage facility for the retention of the consented samples. Should future research on the samples be initiated after study closure, a specific new study protocol will be developed and submitted to relevant Scientific and Ethics Committees following the informed consent requirements.

6. TREATMENT OF PARTICIPANTS

6.1 Description of study treatments

The study treatments (*Artemisia Afra tea infusions*) and control (placebo) will be prepared (quantify, weigh, and package the dry leaves and twigs in tea bags) and labelled in envelopes according to the different study arms at the pharmaceutical Laboratory. The various formulations will be as follows:

Artemisia afra available as infusions containing 5g of Artemisia per liter, will be prepared by adding 5 g dried leaves and twigs of A. afra (in a tea sachet / tea bag) to 1 liter of boiling water, infused for 10 min, and filtered through a sterilized 1 mm mesh.

Artemisia afra available as infusions containing 5g of Artemisia in per 500ml, will be prepared by adding 5 g dried leaves and twigs of *A*. afra (in a tea sachet / tea bag) to 500ml of boiling water, infused for 10 min, and filtered through a sterilized 1 mm mesh.

Flavored Artemisia afra available as infusions containing 5g of flavored Artemisia per liter, will be prepared by adding 5 g of flavored dried leaves and twigs of A. afra (in a tea sachet / tea bag) to 1 liter of boiling water, infused for 10 min, and filtered through a sterilized 1 mm mesh.

Flavored Artemisia afra available as infusions containing 5g of flavored Artemisia per 500ml, will be prepared by adding 5 g of flavored dried leaves and twigs of *A. afra* (in a tea sachet / tea bag) to 500mls of boiling water, infused for 10 min, and filtered through a sterilized 1 mm mesh.

Flavored placebo available as infusions containing flavored inactive substance per liter, will be prepared by adding flavored inactive substance (in a tea sachet / tea bag) to 1 liter of boiling water, infused for 10 min, and filtered through a sterilized 1 mm mesh.

Regular tea placebo will be any tea of choice routinely taken by the selected participants.

Table 5: Various formulation of the study teas and controls.

Drug components	Non-flavored	Flavored
Artemesia afra 5g	Artemesia 5g/ 1liter	Artemesia 5g/ 1liter,
	1.25g/250 ml dose	1.25g/250 ml dose
Artemesia afra 5g	Artemesia 5g/ 500ml,	Artemesia 5g/ 500ml,
	2.5g/250 ml dose	2.5g/250 ml dose
Placebo	Regular tea placebo	Flavored placebo
		250ml dose

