designs, potential gain, and their right to stop at any moment if they accept to enter the study. Then they will be requested to sign a written informed consent. Number of study Fifty-six positive participants have to be enrolled per site, making 112 participants in the whole participants: study. To reach the required number of gametocyte carriers, 635 persons will be RDT tested in Buea (Southwest region) where the expected positive RDT was 9.8.% in Demographic health survey (DHS) 2018 and drop-out rate was set at 10%. In Huye (South region), the expected positive RDT was 14.4% in Malaria indicator survey (MIS)2017 and drop-out rate was set at 10%, hence 432 persons will be RDT tested to reach the required number of gametocyte carriers. Study All students and staff members of the University will be invited to participate in the study. population Participants will be included in the study if in good health (based on physical examination and /Participants medical history), and if they meet all specified eligibility criteria. characteristics/ Inclusion criteria for trial allocation groups Study sites/ Asymptomatic Plasmodium positive students or workers from the selected study universities, aged 18 years and above who provide written informed consent. **Exclusion criteria for trial allocation groups** 1. To have a known hypersensitivity to any ingredients of the tea. 2. Currently taking any malaria drug for prevention or treatment. 3. To have participated in another malaria drug trial or device in the last 1month. 4. To have a history or presence of clinically significant medical, psychiatric, or emotional condition. The study will be conducted at the University of Buea in Cameroon, and the University of Rwanda. All students and staff members of the University will be invited to participate. In the University of Buea, there are about 12,000 students and 973 staff members (500 teachers and 473 administrative /supporting staff. The University of Rwanda (UR), has about 30,445 students and 2,266 staff members (1450 teachers and 816 administrative /supporting) Composition of The study treatments (Artemisia Afra) and control (placebo) will be prepared in the various study and formulations as follows: control Artemisia afra available as infusions containing 5g of Artemisia per liter, will be prepared by adding treatments 5 g dried leaves and twigs of A. afra (in a tea sachet / tea bag) to 1 liter of boiling water, infused for 10 min, and filtered through a sterilized 1 mm mesh. Artemisia afra available as infusions containing 5g of Artemisia in per 500ml, will be prepared by adding 5 g dried leaves and twigs of A. afra (in a tea sachet / tea bag) to 500ml of boiling water, infused for 10 min, and filtered through a sterilized 1 mm mesh. Flavored Artemisia afra available as infusions containing 5g of flavored Artemisia per liter, will be prepared by adding 5 g of flavored dried leaves and twigs of A. afra (in a tea sachet / tea bag) to 1 liter of boiling water, infused for 10 min, and filtered through a sterilized 1 mm mesh. Flavored Artemisia afra available as infusions containing 5g of flavored Artemisia per 500ml, will be prepared by adding 5 g of flavored dried leaves and twigs of A. afra (in a tea sachet / tea bag) to 500mls of boiling water, infused for 10 min, and filtered through a sterilized 1 mm mesh. Flavored placebo available as infusions containing flavored inactive substance per liter, will be prepared by adding flavored inactive substance (in a tea sachet / tea bag) to 1 liter of boiling water, infused for 10 min, and filtered through a sterilized 1 mm mesh. Regular tea placebo will be any tea of choice routinely taken by the selected participants. After preparation, the following doses will be obtained for consumption by participants with

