2.3.2 Secondary objectives

- 1. To assess participants response (treatment efficacy) to varying dose concentrations, dose frequency, length of treatment, and formulation of *Artemisia afra* treatment.
- 2. To identify the most acceptable dose concentration, dose frequency, length of treatment, and formulation (flavor) of Artemisia treatment.
- 3. To assess the safety (ASE) of *Artemisia afra* treatment in participants by dose concentration, dose frequency, length of treatment, and formulation. As a commonly used tea, no toxicity is expected.
- 4. To assess variability of plasmodium test predictive values between mRDT, rtPCR, and direct blood smear observation in asymptomatic persons.

Treatment outcomes

Major outcome

• Decrease in parasite load over time.

Secondary outcomes

- Decrease in gametocyte load in carriers with Artemisia afra tea by dose concentration, dose frequency, length of treatment, and formulation.
- Acceptability (adherence and completion) of *Artemisia afra* treatment by dose concentration, dose frequency, length of treatment, and formulation (flavor).

- Safety (SAEs) of *Artemisia afra* treatment in participants by dose concentration, dose frequency length of treatment, and treatment formulation.
- Absolute increase in Cycle threshold (Ct >20).
- Likelihood and variability in the rate of reservoir elimination with treatment, compliance/ acceptability, and occurrence of side effects /adverse events in different treatment arms.

Treatment endpoints

Primary endpoints

• Proportion of people with decreased gametocyte load after treatment with *Artemisia afra* tea on Day 35 from baseline.

Secondary endpoints

- Level of decrease in gametocyte load (rt-PCR Ct) in the different treatment arms at D7, D14, D28, and D35 from baseline (activity level and optimal dosage schedule).
- Level of decrease in gametocyte load the various treatment arms (rt-PCR Ct) by gender, age, and trial entry parasite load, at D7, D14, D28, and D35 from baseline.
- Absolute increase in Cycle threshold (Ct >20) in various treatment arms at D7, D14, D28, and D35 from baseline.
- Proportion of people in the various treatment arms who respect and complete the prescribed treatment dosages (accepted dosage schedule and drug formulation).
- Proportion of persons on the various arms of treatment who develop clinical symptoms at D7, D14,
 D28, and D35 from baseline.

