3. METHODOLOGY

Study Design: The study is a Phase 2 randomized controlled, partial-blind, parallel group study in plasmodium infected *asymptomatic* adults 18 years and older, with 8 study arms. It will use the adapted Zelen design. The adapted Zelen design uses two steps in the consent process. In the first step, there is an informed consent from all participants for a cohort lifestyle study. After consent is obtained, baseline assessment and screening will be performed, and eligible participants randomly assigned to the different study arms. According to this consent, participants are randomized without knowledge about the detailed protocol. In the second step, only participants from the intervention group will receive the information about the intervention and the second consent will be obtained from them. The participants who will decline to participate to an intervention will continue in the cohort study, as the control group.

Duration of study: The study duration is 35 days (5 weeks) for each participant.

Treatment groups (TG):

TG 1: Group of 8 persons receiving *A. afra* infusions of 5g/1liter of water, 3drinks a day, daily for 1week (7 days) (current recommendation).

TG 2: Group of 8 persons receiving *A. afra* infusions of 5g/500ml of water, 2drinks a day, daily for 1week (7 days) (increase concentration and decrease dose frequency).

TG 3: Group of 8 persons receiving *A. afra* infusions,5g/1liter of water 3drinks a day, weekly for 4weeks (decrease dose frequency and increase length of treatment).

TG 4: Group of 8 persons receiving flavored *A. afra* infusions, 5g/1liter of water 3drinks a day, daily for1week (7 days) (current treatment with improved taste).

TG 5: Group of 8 persons flavored *A. afra* infusions, 5g/500ml of water 2drinks a day, daily for 1 week (7 days) (improved taste, increase concentration and decrease dose frequency).

- **TG 6:** Group of 8 persons receiving flavored *A. afra* infusions, 5g/1liter of water 3drinks a day, weekly for 4weeks (improved taste, decrease dose frequency and increase length of treatment);
- **TG 7**: Group of 4 persons receiving flavored placebo infusions, 5g/liter of water 3drinks a day, daily for 1week (7 days) (improved taste with no active molecule);
- **TG 8**: Group of 4 participants receiving regular tea placebo taken as desired, daily for 1 week (7 days) (Regular tea with no active molecule).

[figure not shown]

Figure 2. Screening and recruitment of study participants

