6.2.2 Concomitant Medications and Vaccines

At each study visit, the investigator will ask the participants about any prescription or over-the counter medication(s) taken since the last visit. Any medications taken at any time during the study period must be recorded on source documents and the case report form with trade and/or generic name, indication, dose, start and end dates. Any treatments and/or medications specifically contraindicated, e.g., any investigational or nonregistered product, any antipyretic/analgesic will be checked at each study visit during treatment period. If any became applicable during the study, it would not require withdrawal of the participant from the study but may determine a participant's evaluability in the per protocol analysis.

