7.1 Solicited and Unsolicited Safety Measurements

Solicited side adverse effects: The term "side effects" refers to signs and symptoms occurring as unintended clinical effects of the treatment whether or not they are harmful (adverse).

Unsolicited Adverse Events: An adverse event (AE) is any undocumented untoward or unforeseen medical occurrence in a participant or clinical investigation participant administered a pharmaceutical product at any dose that does not necessarily have a known causal relationship with this treatment. This definition includes intercurrent illnesses or injuries and exacerbation of pre-existing conditions. In this study, no severe adverse side effects are expected from the treatment, given that Artemisia herbal teas have been used in communities for malaria prevention with no reported toxicity (29). However, since toxicity is always a major concern in clinical trials involving humans, each study participants will be monitored for adverse side effect or adverse events daily, throughout the study period (within 35 days of treatment administration) and where necessary adequate intervention will be provided. Treatment safety data will be collected continuously by the site staff during site and home visits and recorded in

the predefined visit worksheets at Visit Day 7, 14,28 and 35 (i.e, adverse effects). As a consistent method for collecting unsolicited ASE and AEs in this study, the participant will be asked a non-leading question such as: 'Have you acted differently or felt different in any way since receiving the treatment, or since the last study visit?' Occurrence of any adverse side effects or AEs visit within 35 days of treatment will be assessed by healthcare professional at site or home, meanwhile the site staff will continue contacting the participant daily until effects resolution.

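### The TG8 control is labelled inactive but defined as whatever tea the participant usually drinks, and nothing in the protocol clearly keeps Artemisia tea out of it

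*Protocol*

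**What the plan says.** Section 3 (and the synopsis) describes TG8 as "regular tea placebo taken as desired, daily for 1 week (7 days" and adds that it is "Regular tea with no active molecule". Section 6.1 (and the synopsis) defines the drink: "Regular tea placebo will be any tea of choice routinely taken by the selected participants". No list of permitted or excluded teas is given.

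On Artemisia itself, section 2.3.2 says "As a commonly used tea, no toxicity is expected", and section 7.1 says "Artemisia herbal teas have been used in communities for malaria prevention with no reported toxicity".

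The provisions that bear on outside use are these:

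- The second exclusion criterion in the synopsis is "Currently taking any malaria drug for prevention or treatment". Table 3 has nearly the same wording. Neither list mentions Artemisia, herbal tea or past use.
- Section 6.5.1 has investigational or non-registered products taken in the 14 days before treatment recorded. It excludes nobody.
- The section on concomitant medications (numbered 6.2.2) asks about "any prescription or over-the counter medication(s) taken since the last visit". It also checks at each visit in the treatment period for contraindicated items, including investigational or non-registered products. The stated consequence is a possible loss of per-protocol evaluability, not withdrawal.
- Table 4 lists compliance and concomitant medications at each follow-up visit, but not the tea drunk.

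Under the two-step consent in section 3, only TG1 to TG7 are told about the intervention. Those who decline it continue on regular tea as TG8.

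**The concern.** The label and the definition of TG8 do not say the same thing. The label gives a property, namely no active molecule. The definition gives a source, namely the participant's own habit, and does not make the property hold. If Artemisia is a common tea, as the protocol says, some participants' habit may be the study herb.

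What is at stake is the comparison with TG8. Table 5 shows regular tea as the only non-flavored placebo, so TG8 is the natural comparator for the non-flavored arms TG1 to TG3. Artemisia drinking in TG8 would make that control look more like active treatment and push the difference towards no effect, in a study whose aim is to find an activity level. Participants randomized to TG8 receive no intervention information, so they would have no particular reason to avoid Artemisia.

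**Working it through.** **Text check.** Take a participant who drinks Artemisia tea as an ordinary beverage and follow that person through the protocol.

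1. *Entry.* The second exclusion criterion applies only if the site treats the tea as a malaria drug and use is current. Tea drunk for taste, or stopped shortly before Day 0, is not clearly covered.
2. *Allocation to TG8, or declining and joining TG8.* Section 6.1 lets the person continue the usual tea. Only the label in section 3 and the synopsis points the other way.
3. *Follow-up.* The tea is captured if staff or participant regard it as an investigational or non-registered product, or if the observer happens to note it. No item asks for it.
4. *Analysis.* Section 8.2.3 makes the per-protocol population primary for efficacy. It keeps those who took the assigned treatment correctly without major violations, with exclusion criteria settled at a blind review before lock. Usual tea is the assigned treatment in TG8, so the person can be retained as a control.

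**Size of the arm.** Inputs from section 8.1: six arms of 8, two control arms of 4, two sites.

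- Per site: 6 × 8 + 2 × 4 = 56. Both sites: 2 × 56 = 112. Both match the protocol.
- TG8: 4 × 2 = 8, so one participant is 1/8 = 12.5% of the randomized arm. Decliners who join would enlarge the arm and reduce that share.

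**Chance of at least one Artemisia drinker among the 8.** The documents give no prevalence, so q (the share whose routine tea contains Artemisia) is assumed. Formula: 1 − (1 − q)^8.

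| Assumed q | Chance of at least one |
|---|---|
| 5% | 34% |
| 10% | 57% |
| 20% | 83% |

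**Dilution.** Suppose a share c of TG8 responds as an active arm would. Then the observed difference is D × (1 − c), where D is the true active-minus-inert difference in response. The protocol gives no response rates, so two assumed cases are shown: 80% versus 50% (D = 30 points) and 80% versus 20% (D = 60 points).

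| Artemisia drinkers in TG8 | D = 30 | D = 60 |
|---|---|---|
| 0 of 8 | 30 | 60 |
| 1 of 8 | 26.25 | 52.5 |
| 2 of 8 | 22.5 | 45 |
| 4 of 8 | 15 | 30 |

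These figures are upper bounds on the dilution. Table 3 requires a positive RDT and qPCR at entry, so a habitual drinker who is enrolled carries parasites despite the tea and is unlikely to respond like someone newly started on a full assigned schedule.

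**The case against.** The strongest reply is that the passages should be read together: an Artemisia tea does not meet the no-active-molecule label, so the protocol never permits the study herb as placebo. That is a fair account of the intention. It does not help a site, because the definition staff would apply in section 6.1 does not repeat the limit.

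A reader might infer several stronger things that the documents do not support:

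- *That nothing bars Artemisia tea.* The second exclusion criterion names prevention, which is the use section 7.1 describes, and Table 5 lists Artemisia under drug components. A site could reasonably exclude someone drinking it against malaria. The gap is that this depends on the site's reading and leaves out beverage use and past use.
- *That such use would be invisible.* The concomitant check extends beyond ordinary medicines to investigational or non-registered products, and section 6.2 assigns an observer to each arm. Capture is possible but unreliable.
- *That carry-over undermines every arm.* Allocation is random and load is measured at Day 0 before treatment. Prior use is balanced in expectation and mainly adds noise, although chance imbalance is possible in arms this small. TG7 receives a defined inactive infusion, so its assigned drink is not affected.
- *That Artemisia drinking is known to be frequent at these universities.* The remark about common use is made in support of expected safety. The study cited in section 7.1 concerns, by its title, Artemisia annua in a Ugandan community. Neither gives a figure for the two sites.

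**Conclusion.** The point holds in a limited form. The TG8 definition does not secure the property the arm is meant to have, and the existing safeguards cover Artemisia tea only by interpretation. Any resulting bias in the active-versus-TG8 contrast would be towards no effect.

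Its size cannot be stated. Each Artemisia drinker is one-eighth of the randomized arm, but the number of such people is unknown, and the dilution figures rest on assumed response rates and on full response in contaminated controls. The protocol describes a pilot without a formal sample size calculation, and none of its stated figures depends on this point. It is a cheap improvement worth making before enrolment, because a control drink that was not recorded cannot be reconstructed afterwards. It is not a defect that invalidates the design.

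**What to change.** 1. In the synopsis, section 3 and section 6.1, give TG8 one definition: the participant's usual tea, excluding any tea that contains Artemisia. Apply it to decliners who join TG8 as well.
2. In the synopsis criteria and Table 3, state whether Artemisia tea falls under the second exclusion criterion, whatever the reason for drinking it, and how recent use before Day 0 is handled.
3. Add to the visit worksheets, in line with Table 4 and the concomitant medications section, the tea drunk in TG8 and any prior or concurrent non-study Artemisia use in all arms.
4. In section 8.2.3, state how non-study Artemisia use counts for the per-protocol set.

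The cost is an amendment to wording and one or two questions at visits already planned. The downside is that a few habitual users may be lost at screening.

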6.2 Treatment administration

After randomization and allocation, clear education, and demonstrations on how to prepare and consume the treatment will be provided to participants by the site investigator based on their randomization codes. Participants on the trial treatment arms will receive either of the Artemisia infusions of various dosage schedules and formulations, and participants on the placebo arms will drink either a flavored inactive infusion or the regular tea. The participants will take the treatment or placebo orally, under the supervision of one of the investigators (Observers). 8 observers will be assigned to follow up and assist participants on the various treatment arms (1 observer per treatment arm). The observer will encourage compliance to treatment, observe for side effects/ adverse events, and take note of participant's comments/appreciation of the treatment dosages and formulation, throughout the study period. The Observer will also effect home visits to participants when necessary (in case of loss to follow-up and difficulty to contact participant on cell phone).

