Randomization: Prior to treatment, eligible participants will be randomly assigned into the 8 study arms. The randomization method will be a permuted block randomization, with a block size of either 14 or 28 at random, and with a two-to-one allocation ratio for each active arm against two different control arms (2:2:2:2:2:1:1).

Blinding: The participants in the intervention arms will be aware of their assignment to an intervention group but unaware of the treatment assigned to them. The site staff (investigators or observers) will be

aware of assignments to one control arm (regular tea group), but unaware of assignments in the other treatment arms.

Visits/assessment schedules: A total of five study visits will be effected, being one baseline visit on Day 0, and four follow-up visits on Day 7, 14, 28 and 35, from baseline. During the baseline visit plasmodium tests targeting specific parts of the gametocyte genes will be done to determine the participants' initial (baseline) parasite load, and during subsequent visits, follow up control tests (rtPCR and blood smear) will be done, and the gametocyte load recorded, alongside assessments for clinical symptoms and adverse sides effects (if any).

Endpoints The efficacy of each of the treatment dosage schedule will be evaluated on day 7,14,28 and 35 from baseline, based on response to treatment or reservoir elimination rate. Response to treatment will be indicated by an absolute increase in Cycle threshold (Ct >20), or a negative rt-PCR tests results (Ct >40). If the patient misses the follow-up visit, compliance will be noted in the completion worksheet (filled out at end of study) and the parasite load and adverse side effects noted during the last visit considered. No severe side adverse effects are expected from the treatment but since toxicity is always a concern in clinical trials involving humans, participants will be observed for any severe ASEs and withdrawal noted throughout the study duration.

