5.5 Randomization and Blinding Procedures

Randomization: After enrolment of eligible participants, a statistician will randomly assign them in the 8 study arms before treatment administration. The randomization method will be a permuted block randomization, with a block size of either 14 or 28 at random, and with a two-to-one allocation ratio for each active arm against two different control arms (2:2:2:2:2:2:1:1). The treatments will consist of *Artemisia afra* infusions for the 6 trial arms versus flavored placebo infusions and any desired regular tea for the 2 control arms.

Blinding: Neither the participants nor the site staff (investigators or observers) will know to which study arm the participants have been assigned.

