6.3 Treatment supply, labelling, storage, accountability, and disposal

The project coordinators/funders will ensure the following:

- Appropriate supply of the study treatments
- Appropriate labeling of all treatments provided that complies with the legal requirements of each country where the study is being performed.

The investigator must ensure the following:

- Indication of appropriately trained blinded site staff (site manager) to manage the drug supply,
 accountability, prescription, administration, and observation.
- Acknowledge receipt of the treatment at the site, including confirmation that the treatments were received in good condition, remained within the appropriate temperature range during shipment

- from production site to the designated storage location, and ensure appropriate storge conditions in accordance with the manufacturer's recommendations.
- Proper storage of treatment: Storage in a secure, locked, temperature-controlled location according
 to the instructions specified on the labels, and appropriate record keeping and inventory, including
 regular documentation of adequate storage temperature.
- Appropriate use of the treatments only in accordance with the approved protocol.
- Complete record keeping of treatment use, wastage, or destruction, including documentation of number of doses destroyed, date of destruction, method of destruction, and name of individual performing destruction.

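### Giving each arm its own observer aliases observer with arm for adherence and adverse events, and the protocol's blinding statements contradict each other and the visible regimens

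*Protocol*

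**What the plan says.** Section 6.2 (Treatment administration) fixes the roster: "8 observers will be assigned to follow up and assist participants on the various treatment arms (1 observer per treatment arm"). Intake takes place "under the supervision of one of the investigators (Observers"). The duties are wide: "The observer will encourage compliance to treatment, observe for side effects/ adverse events", and the observer also notes the participant's "appreciation of the treatment dosages and formulation, throughout the study period". The protocol does not say whether 8 is the total or the number per site. It describes no rotation of observers across arms and no separate assessor for adherence or adverse events.

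Three places deal with the blinding of staff:

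- Section 5.5: "Neither the participants nor the site staff (investigators or observers) will know to which study arm the participants have been assigned".
- Section 3, Blinding: site staff are "aware of assignments to one control arm (regular tea group), but unaware of assignments in the other treatment arms".
- Section 6.3 asks for "Indication of appropriately trained blinded site staff (site manager) to manage the drug supply", and extends that role to administration and observation.

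Section 2 lists adherence and completion, clinical symptoms, side effects and adverse events, and withdrawals as secondary endpoints by treatment arm. Section 8.2.3 makes the per-protocol population, which requires that every dose was correctly received, the primary population for all efficacy objectives.

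**The concern.** Adherence and reported adverse events depend partly on who encourages and who asks. When each arm has its own observer, a persuasive or lax observer can make a regimen look more or less acceptable, or safer or less safe, than it is. The primary objective includes finding the accepted dose, frequency, length and flavour, so these endpoints matter to the trial's purpose although they rank as secondary. Adherence also governs entry to the per-protocol set, so observer differences can reach the efficacy results indirectly.

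The aliasing is a rule of conduct. Once participants have been followed under it, no later analysis plan can supply the missing within-observer comparisons.

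The blinding text raises a second, separate question: whether its statements agree with each other and can be true of a person who watches the tea being drunk.

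**Working it through.** **Arm sizes (section 8.1).** Six active arms of 8 and two control arms of 4 give 6×8 + 2×4 = 56 per site and 2×56 = 112 overall, as stated. Over both sites an active arm has 16 participants and a control arm has 8.

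**What can be estimated.** For a model with arm, observer and site, the degrees of freedom (df) follow from the rank of the design matrix:

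| Roster | Arm df after adjusting for observer | Observer df after arm and site | Residual df |
|---|---|---|---|
| 8 observers in total, one per arm | 0 | 0 | 103 |
| 8 per site, one per arm | 0 | 7 | 96 |
| 8 in total, each following a block of 14 (4 per site) | 7 | 6 | 97 |

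Under either reading of section 6.2, no arm contrast survives adjustment for fixed observer effects. With 8 per site, observer variance can be estimated, but on only 7 df.

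**Illustrative size.** The protocol gives no ICC for observers, so 0.01 to 0.10 is assumed. The calculation also assumes a two-sided 5% t-test on a continuous outcome with no treatment effect. With one observer per arm, the test sees only the within-observer variance (1 − ICC), so the true variance of the difference exceeds the estimated one by

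F = 1 + 2·ICC / [(1 − ICC)(1/n₁ + 1/n₂)]

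and the true error is P(|t| > t_crit/√F).

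- 16 v 16, ICC 0.10: F = 1 + 0.20/(0.90 × 0.125) = 2.78; 2.042/√2.78 = 1.225 on 30 df, giving 23%.
- 16 v 8, ICC 0.10: F = 1 + 0.20/(0.90 × 0.1875) = 2.19; 2.074/√2.19 = 1.403 on 22 df, giving 17%.

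Simulation with 100,000 runs per cell agrees and adds the case of two observers per arm:

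| ICC (assumed) | One observer, 16 v 16 | One observer, 16 v 8 | Two observers, 16 v 16 | Two observers, 16 v 8 |
|---|---|---|---|---|
| 0 | 5.1% | 4.9% | 4.9% | 5.0% |
| 0.01 | 6.7% | 6.2% | 5.8% | 5.6% |
| 0.05 | 14.4% | 11.0% | 9.4% | 7.7% |
| 0.10 | 22.9% | 17.4% | 13.6% | 10.4% |

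**Blinding, text against text.** Section 5.5 allows no exception; section 3 excepts the regular-tea arm. Both cannot hold.

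**Blinding, text against regimens.** From the arm descriptions in section 3, drinking schedule alone sorts the arms into {TG1, TG4, TG7}, {TG2, TG5}, {TG3, TG6} and {TG8}. Adding flavour identifies six of the eight arms uniquely; only TG4 and TG7 share both schedule and flavour. Someone who supervises intake and records views on dosage and formulation will see these features whatever the roster.

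**The case against.** **The roster does not cause the unblinding.** A reader might infer that one observer per arm is what makes the stated blinding impossible. The documents do not support that. The regimens differ visibly and would reveal themselves to observers crossed over arms too. Observers could stay masked to active v placebo between TG4 and TG7 if arms are coded and the flavour hides the taste. Participant masking does not depend on the roster, and the design is declared partial-blind. This objection stands in full, so blinding is treated here as a separate fault.

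**Some analysis is possible.** It is too absolute to say that nothing can be done. With 8 observers per site, a random observer effect can be fitted, weakly. The outcomes are also worded by regimen factor: flavoured v unflavoured pools TG4–TG6 against TG1–TG3, so each side has at least three observers. This softens the problem for pooled factors but does not rescue comparisons between single arms, which is how the endpoints are worded.

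**The error rates are assumed.** Section 8.3 names no pairwise adherence test, only descriptive percentages and a linear mixed model, and the study is a pilot. One observer covering both countries is also hard to picture. All of this is fair: the rates are illustrations, and the aliasing does not depend on them.

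**Safeguards exist.** There is a standard non-leading question with predefined worksheets and assessment by a health professional (7.1), DAIDS grading by the investigator (7.1), common training (9.2) and source verification (9.3). These may shrink observer differences but cannot separate them from arm. Section 6.2 itself calls observers investigators, so investigator grading is not clearly independent.

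**Conclusion.** The point holds for adherence, symptoms, adverse events and per-protocol membership. As written, observer is aliased with arm, or nested in it with at best 7 df for observer variance. That follows from section 6.2 alone and needs no assumption.

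The consequence in numbers is unknown. The error rates in the working hold only for an ICC of 0.01 to 0.10 and a continuous outcome, whereas adherence and adverse events are proportions.

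It would go too far to conclude that the rtPCR endpoint itself is compromised: the observer does not read it, and the only route shown is through adherence and the per-protocol set.

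Sections 3 and 5.5 contradict each other on the regular-tea arm, and neither they nor section 6.3 fits supervised intake of visibly different teas. This unblinding comes from the regimens and will remain after the roster is changed.

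**What to change.** **Roster (6.2).** Keep the same observers but cross them with arms within site. If 8 is the total, 112/14 = 8, so each can follow one complete randomisation block of 14, four observers per site, and every observer covers all eight arms (two per active arm, one per control arm). Section 5.5 also allows blocks of 28; these need sharing between two observers so that each still receives a full set of 14. If 8 per site is meant, 56/8 = 7 participants each cannot cover eight arms; four observers per site should then each take a block. State which number is meant.

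**Analysis (8.3).** Include observer in the adherence and adverse-event models.

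**Blinding (3, 5.5, 6.3).** Replace the three statements with one: observers can see schedule and flavour, and masking of observers is feasible at most for active v placebo between TG4 and TG7. State that laboratory staff are blinded only if the sponsor confirms it; the protocol describes coded samples but no laboratory blinding.

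**Cost.** Each observer must be trained on all preparations and will see several regimens side by side. No extra staff are needed. The roster must change before enrolment.
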